That human migraine can be treated effectively with episodic injections of anti-CGRP antibodies begets the question whether these newly prescribe-able medications can be repurposed for other trigeminal pain conditions and the related glossopharyngeal cranial nerve pain which are known to involve neurogenic inflammation. Another pain condition with poor treatment options for sufferers is fibromyalgia, especially fibromyalgia with associated small fiber neuropathy which leads to systemic de-afferentiation of patients' sensory system. In this condition, there is strong evidence for presence of neurogenic inflammation, and it is a rational concept that neurogenic inflammation contributes to disease pathogenesis and especially to the dominating clinical symptom of pain.

We propose to treat patients (targeting enrollment of n=20) who suffer from trigeminal or glossopharyngeal nerve pain in the context of painful small fiber neuropathy. We predict that recruitment of these patients will not be a challenge in the PI's clinics, based on previous experience and ongoing referral practice. Primary criterion is to establish an excellent safety profile that recapitulates the favorable data recorded in migraineurs. The primary pain-related objective is reduction of pain and reduced use of rescue and other anti-pain medications.

Secondary pain-related objectives are improvement of circadian rhythm impairment by galcanezumab, improvement of serum markers for chronic inflammation including protein/peptide as well as small non-coding RNA molecules, and discovery of DNA polymorphisms that predispose treated patients to accentuated responses of either lack of response or particularly potent response.

Clinical Collaborators

[name] MD, Duke Neurology
[name] MD

Hypothesis/ Purpose

We hypothesize that the proposed galcanezumab regimen will be found safe in our patient population, and that provisional evidence of its effectiveness will become apparent. We envision galcanezumab to target neurogenic inflammation in the trigeminal territory and neurogenic inflammation associated with small fiber neuropathy/fibromyalgia.

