Treatment with a CGRP-neutralizing antibody, galcanezumab in this specific patient group, being seen in the PI's clinics on a regular basis, is rooted in the rationale of unmistakable presence of clinical signs of neurogenic inflammation in the painful territory, such as episodic swelling combined with redness/hyperemia, also relief by external cold application which typically patients with trigeminal or glossopharyngeal nerve pain abhor.

Primary Outcome Measures

Primary criterion is to establish an excellent safety profile that recapitulates the favorable data recorded in migraineurs. The primary pain-related objective is reduction of pain and reduced use of rescue and other anti-pain medication.

Inclusion Criteria

- G50.1 diagnosis (can encompass an add-on G50.0 and other headache G43.... codes), or G52.1 diagnosis code (with explicit mentioning of pain of glossopharyngeal origin) **AND** small fiber neuropathy diagnostic codes G63.3, G60.8, G62.8 (can encompass fibromyalgia diagnostic code M79.7)
- 18-80 years old
- not allergic to galcanezumab and other hu mAb biologics

Exclusion Criteria

- allergic to galcanezumab and other hu mAb biologics
- pregnancy

Study Design / Overview

We propose to treat patients open label for 12 weeks, with galcanezumab, supplied by Eli Lilly, as add-on to all other therapeutic measures. We propose to use a 240mg/120mg/120mg regime, with subcutaneous (self-)injections every 4 weeks.

To reflect pain experienced by patients, the primary read-out is pain level on a 0-10 visual analog scale. We will be prompting patients to record a daily summary read at the end of each day.

[figure not shown]
The second criterion is reduction of intake of anti-pain medication (rescue PRN or regular) which the patients will record.

Chronic pain, especially fibromyalgia pain combined with trigeminal or glossopharyngeal nerve pain, is a potent disruptor of circadian rhythm. We strongly believe that this is an important and hitherto under-appreciated contributor to individual disease burden. Therefore, the third criterion is assessment of circadian rhythm function. We will assess this by having the patient rate subjectively how energetic they feel during awake day-time. Wearable activity monitors will be used to address how many hours patients sleep per

24h period, with detailed focus on total duration of sleep/rest and duration of night-time sleep only.

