We also expect that the proposed studies will be very important for guiding future, more in-depth studies involving larger patient cohorts, placebo-controlled/double-blinded studies, which will possibly lead us toward a personalized-medicine approach.

Study Design Detail

1) Schedule of Activities over Time

2) Blood draw: detailed analysis

Before treatment, and at 45th, 75th, 105th and 135th day of treatment, we propose to assess the following blood parameters, related to pain-associated biomarkers in the systemic circulation.

For this, we propose to study cytokine/chemokine pain- and inflammation markers in patients' serum, using commercially available protein multiplex detection assays. In serum, the following 39 cytokines/chemokines/lipid mediators/peptides will be measured: EPO, GM-CSF, IFN- γ , IL-1 β , IL-2, IL-4, IL-5, IL-6, IL-9, IL-10, IL-12/IL-23p40, IL-12p70, IL-13, IL-15, IL-16, IL-17A, IL-17A/F, IL-17C, IL-17E/IL-25, IL-17F, IL-21, IL-22, IL-23, IL-27p28/IL-30, IL-31, IL-33, IP-10, KC/GRO, MCP-1, MIP-1 α , MIP-1 β , MIP-2, MIP-3 α , TNF- α , VEGF-A, TGF- β , CGRP, Resolvin-D1, Prostaglandin-E2. For these measurements, we will be using a human 35-plex ELISA (U-PLEX Biomarkers) and single ELISAs (Signosis; Cayman).

These are key mediators and indicators of pain and inflammation. We believe it will be feasible to conduct these assays. For each marker there is sufficient evidence supporting its role in pro-algesic inflammation or organismal response to tissue damage. We are

convinced that their ensemble will prove a powerful source of mechanistic data that will elucidate treatment responses to galcanezumab in our patient population.

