time course of pain metrics reported during the treatment period will be compared with metrics during the run-in baseline. The covariance matrix describing the nature of correlations between repeated measures will be selected based on Akaike information criterion and Bayesian information criterion, as guided by our statistics software, SAS/STAT15.1. p-values <0.05 will be considered statistically significant. Effects of treatments will be investigated with the introduction of treatment as a binary covariate (we will evaluate the effects of pre- and post-treatment in two different models).

Patients' anti-pain treatment response will be correlated with blood markers for pain, inflammation and miRNA, and also for genomic markers. This approach will be pursued in order to identify candidate biomarkers that pre-dispose patients to experience an effective or non-effective treatment response. In case of recording any particular safety-related parameters, correlation of these markers to safety metrics will also be conducted. Association between molecular biomarkers and pain- and activity-related metrics will be evaluated (i) at each time point separately using a linear regression model; (ii) by modeling the association across all time points and including time covariate in the linear regression model. The ensemble of these approaches will help determine the periods when pain or activity-related metrics and molecular markers co-evolve and become highly correlated.

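### Post-dose serum CGRP is analysed as an ordinary inflammation marker although the study drug binds CGRP, so as specified its change is not interpretable as a change in inflammation

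*Combined protocol and SAP*

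**What the plan says.** The Hypothesis/Purpose section states the intervention: "Treatment with a CGRP-neutralizing antibody, galcanezumab". The Study Design/Overview gives the regimen as a "240mg/120mg/120mg regime, with subcutaneous (self-)injections every 4 weeks".

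Section 2 (Blood draw) sets the sampling times, "Before treatment, and at 45th, 75th, 105th and 135th day of treatment", and says that "the following 39 cytokines/chemokines/lipid mediators/peptides will be measured". The list closes with "CGRP, Resolvin-D1, Prostaglandin-E2". The assays are a 35-plex ELISA and single ELISAs, and the whole panel is described as indicating pain and inflammation. CGRP is not set apart.

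The panel then has three uses:

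- The Abstract makes a secondary objective of "improvement of serum markers for chronic inflammation including protein/peptide as well as small non-coding RNA molecules".
- Section 2 looks for associations between high or low response and any biomarker measured, peptides included.
- Section 11 regresses pain and activity metrics on the markers at each time point separately, and again "by modeling the association across all time points and including time covariate in the linear regression model".

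The document does not say whether the CGRP assay reads free, bound or total peptide. It plans no check for drug interference, no measurement of antibody concentration and no separate handling of CGRP after dosing.

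**The concern.** A neutralizing antibody works by binding its target. Once it is in the serum, an immunoassay for that target may read low, if the antibody masks the site the assay needs, or high, if the assay also detects antibody-bound peptide that is cleared slowly. Either shift can occur with no change in neurogenic inflammation. The other 38 markers are not the drug's direct target, so a rule that is reasonable for them is not reasonable for CGRP.

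The trial has one arm, so no untreated series exists against which a binding effect could be recognised. A drug-driven shift in CGRP that coincides with any before-after change in pain could be read as support for the trial's mechanism and carried into the larger studies that this pilot is meant to guide.

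**Working it through.** **Reproducing the plan's figure.** Counting the list in section 2 gives 39 analytes, as stated. The first 35 (EPO to VEGF-A) match the size of the 35-plex. CGRP is number 37, so by position it is one of the 39 − 35 = 4 single-ELISA analytes.

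**How many CGRP values are post-dose.** There are 5 draws, 1 before treatment and 4 after dosing starts. With 20 completers that is 20 × 4 = 80 of 20 × 5 = 100 samples.

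**How much drug may be present.** Injections every 4 weeks put the doses of 240, 120 and 120 mg on treatment days 0, 28 and 56. The documents give no half-life, so 14 to 35 days is assumed. Residual amount = sum of dose × 0.5^(days since dose / half-life), shown as a share of the 240 mg first dose.

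The draw days can be read in two ways. Section 2 calls them days of treatment, yet days 105 and 135 lie beyond 12 weeks (84 days) and beyond the 90-day treatment period of section 11. They may instead be study days that include a 28- to 30-day run-in. The passages need to be reconciled; both readings are shown.

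| Draw | Days since latest injection, literal | Residual, literal | Days since latest injection, study day | Residual, study day |
|---|---|---|---|---|
| 45 | 17 | 32–77% | 15–17 | 43–74% |
| 75 | 19 | 27–77% | 17–19 | 29–77% |
| 105 | 49 | 6–42% | 19–21 | 24–77% |
| 135 | 79 | 1–23% | 49–51 | 6–42% |

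The lowest cell, literal day 135 at a 14-day half-life, is 240 × 0.5^(135/14) + 120 × 0.5^(107/14) + 120 × 0.5^(79/14) = 0.3 + 0.6 + 2.4 = 3.3 mg. At 35 days the same draw has about 56 mg. Days 45 and 75 are on drug under every reading; day 135 ranges from nearly cleared to substantial.

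**What binding does to a free-peptide reading.** With binding sites in large excess, the free share is 1/(1 + r), where r is the ratio of binding sites to the dissociation constant. For assumed r of 1, 10 and 100 it is 50%, 9% and 1%. An assay that reads total peptide would behave differently and could rise.

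**What the across-time regression does.** Take a shift that is 0 at baseline and equal at all four later draws, with baseline placed at day 0 (an assumption). The draw times 0, 45, 75, 105 and 135 have mean 72 and a sum of squared deviations of 10,980.

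- Total sum of squares of the step: 5 × 0.8 × 0.2 = 0.80.
- Part explained by linear time: 72² / 10,980 = 0.47, where 72 is the cross-product of the step with the centred times.
- Part left over: 0.80 − 0.47 = 0.33, or 41%.

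So linear time leaves 41% of a common step in CGRP, and 41% of any matching step in pain. The two remainders correlate. Categorical time removes a common step completely.

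Simulations agree: 20 patients, 5 draws, a post-dose assay shift of 3 SD, a drop in pain and no true association (all assumed). With categorical time, about 5% of runs were falsely significant. With linear time the share was about 34% to 83% over the settings tried. It depends on the assumed pain drop: a rerun with a drop of only 0.5 SD gave about 12–13%.

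**The case against.** The case for leaving the plan alone has four parts.

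*The assay is unknown.* A reader might infer that post-dose CGRP cannot be used at all. The documents do not support that. They do not give the assay's epitope or the fraction it reads, so they support only that the values are not interpretable as specified. This part of the objection stands.

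*Not every draw is affected.* A reader might infer that CGRP is compromised at every draw, or at every post-dose draw through day 135. The baseline sample is antibody-free and serves section 11's aim of finding markers that predispose to response. The day-135 conclusion needs figures that the documents do not give. If 3.3 mg remains, and one assumes a 150 kDa antibody with two sites, a volume of 4–10 L, bioavailability of 0.5–1 and CGRP at 100 pg/mL (about 26 pM), sites are about 2–11 nM, an 84- to 419-fold excess over the peptide. Excess alone does not fix the bound share: the free share is 8–31% at an assumed dissociation constant of 1 nM and 1–4% at 0.1 nM. So day 135 can be presumed neither clean nor compromised.

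*Section 11 promises no before-after test of CGRP.* Its before-after comparisons cover pain, medication and circadian metrics; markers enter through correlation and regression. A reader might infer that the plan is bound to report a CGRP change and a false CGRP-pain link. The change is implied only by the general objective in the Abstract, and the false link depends on how time is coded, which section 11 leaves open. Both claims must be conditional.

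*Importance.* The laboratory work is described as ancillary, and no section names CGRP as the key mechanistic marker. This stands and limits the grade.

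What does not fall is the core: the drug binds the analyte, and the plan has no rule that treats this analyte differently.

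**Conclusion.** Wrong as written, minor. Applied as it stands, the plan would allow drug-target binding to be read as a change in inflammation for one marker of 39, at four of its five draws. This follows from the documents alone: what the drug targets, when blood is drawn and how the panel is used.

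The direction and size of the shift are not known. They rest on the assay format, the half-life, the binding affinity and the reading of the draw days, none of which the documents settle. The pooled-regression artefact arises if time is linear and both CGRP and pain step at dosing; it does not arise from a common shift if time is categorical. Pain, medication-use and safety outcomes, the other 38 markers and baseline CGRP are unaffected.

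**What to change.** In sections 2 and 11:

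- Use the pre-dose CGRP value as the candidate predictor of response.
- Exclude post-dose CGRP from the marker-improvement objective, from the responder associations as an inflammation marker, and from the inflammation regressions, both at single time points and across time.
- Report any post-dose CGRP values separately and descriptively as drug-target binding, stating which fraction the assay detects with galcanezumab present.

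A laboratory check of the assay with drug added to baseline serum would help to establish that fraction, but it is optional and the fix does not depend on it.

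The cost is a few sentences of SAP and laboratory wording. No visit, sample or treatment rule changes. The downside is that post-dose CGRP is lost as an exploratory inflammation series.

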Before treatment, there will be a 4 week observation-only period, and another one 8 weeks post-treatment, so that the total study period will be 6 months.

We aim for 20 patients to be included in this study.

see more detailed graphics in the next section

In terms of ancillary, laboratory-based studies, we intend to draw blood before treatment and at the 45-, 75-, 105- and 135-day of treatment time-points. We will measure cytokine/chemokine/lipid pain- and inflammation markers in patients' serum, also determine microRNA in their serum, and genomic DNA polymorphisms, the latter only at baseline. Please see next section for more detail.

To establish safety of the anti-CGRP treatment in this patient cohort, blood draw at baseline and at the 45-, 75-, 105- and 135-days of treatment time-points will also include routine systemic sentinel/surveillance markers, namely comprehensive metabolic panel and complete blood count with differential, and complete urinalysis. No more than 45 ml of blood will be collected at any given visit.

In terms of additional safety parameters, we propose an open, patient-kept side-effect log, plus home-based recordings of blood pressure, heart rate and weight at a frequency of 2x/week.

We will set up a data and safety monitoring board for proper management and oversight of data handling and patient safety-related issue; see next section.

[figure not shown]
We expect to observe effective treatment, at least in a significant subgroup of patients. Effectiveness of treatment, also magnitude of any observed therapeutic effect will be correlated with the pain/inflammation proteinaceous, lipid and RNA-based biomarkers in patients' serum, also with any polymorphisms in the patients' genomic DNA.

We also expect galcanezumab treatment to show another record of safe treatment, our expectation sculpted by analysis of in-depth data from treatment of migraineurs. Yet we will remain vigilant and implement the proposed safety sentinel measures in order not to miss adverse effects. This appears prudent because trigeminal or glossopharyngeal nerve pain plus small-fiber neuropathy is a different underlying disorder than migraine, likely representing a higher prevalence in peri-menopausal female patients. We also believe it is likely that level of chronic pain suffering-associated stress will be higher in our study population than in migraineurs.

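### The serum-marker list includes names normally used for rodent chemokines (KC/GRO, MIP-2) and omits IL-8, although the kit is called human; list and kit must be reconciled before any assay is run

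*Combined protocol and SAP*

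**What the plan says.** Study Design Detail, section 2 (Blood draw), fixes the specimen: "we propose to study cytokine/chemokine pain- and inflammation markers in patients' serum". The Study Design overview says the same: "We will measure cytokine/chemokine/lipid pain- and inflammation markers in patients' serum". Section 2 then gives a count, "the following 39 cytokines/chemokines/lipid mediators/peptides will be measured", and spells out every entry. Among them is the sequence "IP-10, KC/GRO, MCP-1"; MIP-2 comes a few entries later. The interleukins pass from IL-6 directly to IL-9.

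The assays are named in one sentence: "For these measurements, we will be using a human 35-plex ELISA (U-PLEX Biomarkers) and single ELISAs (Signosis; Cayman". The section gives no catalogue number, no table of which marker is run on which kit, and no check that each assay is validated for human serum. It says only that the assays are thought feasible.

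The Abstract makes improvement of serum inflammation markers a secondary objective. Section 11 (Brief Statistical Analysis Plan) correlates the markers with treatment response and regresses pain and activity metrics on them, at each time point and across time points.

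**The concern.** A prespecified marker list should tell the analyst exactly which proteins enter the models. Here the list and the kit description point in different directions. KC and MIP-2 are names ordinarily given to rodent neutrophil chemokines. IL-8 is a standard human neutrophil chemokine with no direct mouse or rat counterpart. One odd name could be a slip. Two such names, together with the missing human chemokine, in a block that exactly fills the multiplex, raise the question whether the list was taken from a panel for another species.

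Two things are at stake. If a human kit is run, two listed markers have no clear identity, and whatever is reported in their place was not specified in the plan. If the kit actually ordered follows the list and is not made for human samples, signal of doubtful specificity would enter the regressions in section 11 with nothing in the plan to flag it. Serum is finite (the overview caps each blood draw at 45 ml), so a wrong assay may not be repeatable.

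**Working it through.** **Inputs from the documents**

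- Stated number of markers: 39 (section 2).
- Multiplex size: 35, labelled human (section 2).
- Blood draws: 5, namely baseline and days 45, 75, 105 and 135 (overview and section 2).
- Patients: 20 completers (section 11).

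**Step 1: reproduce the stated count.** Counting the comma-separated entries gives 39, all distinct, so the plan's figure is right.

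**Step 2: allocate entries to kits.** The plan does not do this, so it is inferred. The list is in alphabetical and numerical order from EPO to VEGF-A, which is entry 35. The order breaks at entry 36, TGF-beta, which is followed by CGRP, the resolvin and the prostaglandin. Thus 35 multiplex entries + 4 single-assay entries = 39, which fits the two assay types named.

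**Step 3: locate the doubtful entries.** KC/GRO is entry 28 and MIP-2 is entry 32. Both lie inside the block of 35. IL-8 is nowhere among the 39.

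**Step 4: size.** Planned values = markers × draws × patients, assuming one value per marker per draw and no missing samples.

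| Case | Markers | Values | Share |
|---|---|---|---|
| All listed markers | 39 | 39 × 5 × 20 = 3,900 | 100% |
| Human kit run: the two named entries | 2 | 2 × 5 × 20 = 200 | 2/39 = 5.1% |
| Kit matching a non-human list run: upper limit | 35 | 35 × 5 × 20 = 3,500 | 35/39 = 89.7% |

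The shares do not depend on the number of draws or patients. The four markers outside the multiplex are untouched in every case. The second row follows the plan's own statement that the kit is human. The third is conditional on a kit that the plan does not say it will use.

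**The case against.** The strongest reply is that the only statement on species in the plan is that the kit is human and the serum is the patients'. Nothing mentions a rodent assay, and the kit's contents are not in the documents. The count reconciles. KC/GRO itself contains GRO, and both entries may be loose labels for human chemokines, in which case two names need correcting and no measurement is lost. Nothing promised IL-8, so its absence is not in itself a fault. The overview calls the laboratory work ancillary, and section 11 describes a search for candidate biomarkers with no decision resting on any single marker.

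Most of this stands, and it limits the point. A reader might infer that the 35 analytes are a rodent panel, that the 39 markers therefore cannot be measured, and that about 90% of the values would be lost. The documents do not support this. The first step needs a manufacturer's list that they do not contain, the last assumes a kit other than the one named, and four markers lie outside the multiplex in any case.

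The reply does not remove the inconsistency. Even on the mildest reading, a reader cannot tell which human proteins KC/GRO and MIP-2 stand for, and the plan offers no kit table or validation step that would show it.

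**Conclusion.** The marker list and the human kit named with it are inconsistent as written. If a human kit is run, at least 2 of 39 entries (200 of 3,900 planned values, 5.1%) are not identifiable as listed. If a kit matching a non-human list were run, up to 35 of 39 would be in doubt. The documents cannot settle which applies, so the supportable range is 2 to 35, with the lower end following from the plan's own description of the kit.

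This rests on two assumptions: that KC/GRO and MIP-2 carry their usual rodent-type meaning, and that the first 35 entries are the multiplex. The absence of IL-8 is supporting evidence only.

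The effect is confined to the serum-marker secondary objective and the biomarker associations. Safety, the pain endpoints and the sample size of 20 are unaffected. The point is worth acting on because the stated list is itself inconsistent and the correction is cheap.

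**What to change.** Before any assay is run:

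1. Name the human panel, with its catalogue number, and replace the list in section 2 with that panel's analytes plus the single assays, in a table showing which marker is run on which kit.
2. Replace KC/GRO and MIP-2 with the human chemokines that the panel measures, or remove them, and restate the marker count.
3. Confirm from the kit documentation that each assay is validated for human serum. State in section 11 that any assay that is not will be excluded from the biomarker analyses.
4. Optionally add IL-8 if the panel offers it.

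The cost is protocol wording and a check of the kit order. No additional blood, visits or patients are needed. A human panel is assumed to cost about the same; the documents give no prices.

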- Modifications of the study protocol based upon the review of the safety data;
- Suspension or early termination of the study because of serious concerns about subjects' safety.

Confidentiality must always be maintained during all phases of DSMB review and deliberations. DSMB members must maintain strict confidentiality concerning all privileged study results provided to them.

DSMB membership reflects appropriately involved medical disciplines, also takes into account the pilot nature of our study.

No member of the DSMB has direct involvement in the conduct of the study. No member has financial, proprietary, professional, or other interests that may affect impartial, independent decision-making by the DSMB.

Meetings are set once a year and will be scheduled more frequently in case adverse effects occur more than 2x/ month of a severe AE per quarter.

The initial DSMB meeting should occur preferably before the start of the trial or as soon thereafter as possible. At this meeting the DSMB will discuss the protocol and its roll-out, mandatory triggers set for data review or analyses. Guidelines will address stopping the study for safety concerns.

Once a study is implemented, the DSMB will convene as often as necessary, but at least once annually, to examine the accumulated safety and enrollment data, review study progress, and discuss other factors (internal or external to the study) that might impact continuation of the study as designed. A DSMB meeting may be requested by DSMB members, the PI, the Duke University IRB, or study Principal Investigator at any time to

discuss safety concerns. Decisions to hold ad hoc meetings will be made by the PI and DSMB Chair. Meetings may be held by conference calls or videoconferences or as face-to-face meetings. In the event a DSMB member cannot attend a meeting, he/she may participate by conference call, in addition can provide written comments to the DSMB Chair for consideration at the meeting.

4) Necessary patient equipment/materials to generate data-points when home

Patients will be provided with a 200-page paper booklet.

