After the informed consent form (ICF) is signed, study site personnel will record via case report form (CRF) the occurrence and nature of each subject's preexisting conditions, including clinically significant signs and symptoms of the pain condition under treatment in this study. In addition, site personnel will record any new conditions as AEs. Investigators should record their assessment of the potential relatedness of each AE to galcanezumab and/or protocol procedure via CRF.

The PI will interpret and document whether or not an AE has a reasonable possibility of being related to galcanezumab, its injection, or a study procedure, taking into account the disease, co-morbid conditions, concomitant treatment or pathologies.

A “reasonable possibility” means that there is a cause and effect relationship between galcanezumab, and/or study procedure and the AE.

The PI answers “yes/no” when making this assessment.

Planned surgeries and nonsurgical interventions should not be reported as AEs unless the underlying medical condition has worsened during the course of the study.

If galcanezumab is discontinued for a given patient as a result of an AE, study site personnel must report this to the Duke IRB via CRF, clarifying if possible, the circumstances leading to discontinuations of treatment.

A severe AE (SAE) is any AE from this study that results in one of the following outcomes:

- death
- initial or prolonged inpatient hospitalization
- a life-threatening experience (that is, immediate risk of dying)
- persistent or significant disability/incapacity
- congenital anomaly/birth defect
- important medical events that may not be immediately life-threatening or result in death or hospitalization but may jeopardize the patient or may require intervention to prevent one of the other outcomes listed in the definition above. Examples of such medical events include allergic bronchospasm requiring intensive treatment in an emergency room or at home, blood dyscrasias or convulsions that do not result in inpatient hospitalization, or the development of drug dependency or drug abuse.

All AEs occurring after signing the ICF are recorded in the CRF and assessed for fulfilling criteria of SAE. SAE reports are forwarded to the Duke University IRB. For each SAE, the Duke University IRB safety commission will decide within 48h whether the case will be forwarded to Eli Lilly immediately.

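### The automatic trigger for an early DSMB meeting cannot be applied as written, and the SAE notification pathway has no step that informs the DSMB

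*Combined protocol and SAP*

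**What the plan says.** **Meeting schedule and trigger (section 3, Data Safety Monitoring Board).** The default is annual: "Meetings are set once a year and will be scheduled more frequently". The condition that brings an earlier meeting is worded as follows: "in case adverse effects occur more than 2x/ month of a severe AE per quarter". The same section adds that, once the study runs, "the DSMB will convene as often as necessary, but at least once annually".

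**Meetings on request (section 3).** "A DSMB meeting may be requested by DSMB members, the PI, the Duke University IRB, or study Principal Investigator at any time". The stated purpose is to raise a safety matter. Whether such a meeting takes place is settled jointly: "Decisions to hold ad hoc meetings will be made by the PI and DSMB Chair".

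**Matters left to the first meeting (section 3).** "At this meeting the DSMB will discuss the protocol and its roll-out, mandatory triggers set for data review or analyses". Guidelines on stopping for safety are also left for later. That meeting is preferred, but not required, before the trial starts.

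**SAE pathway (section 7, Risks and Adverse Reactions).** "A severe AE (SAE) is any AE from this study that results in one of the following outcomes"; the list that follows is the usual one for serious events. "SAE reports are forwarded to the Duke University IRB", and the IRB must be alerted within 24 hours. The IRB's safety commission decides within 48 hours whether the case goes to the manufacturer at once. The closing paragraph of section 7 describes communication among the PI, the clinical team, the IRB and the manufacturer. The DSMB is not mentioned.

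**The concern.** A trigger needs an event, a count, a window, a unit (patient or study) and someone who counts. The section 3 sentence gives two events and two windows with no working conjunction, and neither a unit nor a counter. Two people applying it in good faith to the same AE listing could disagree on whether a meeting is due.

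The second gap adds to the first. Section 3 has the DSMB review interim and cumulative AE data but gives no delivery timetable outside meetings, and section 7 sends it no individual SAE notice. Prompt DSMB awareness of an SAE therefore depends on someone else deciding to involve it.

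At stake is the trial's primary criterion, which is safety. A patient is on study for about half the interval between annual meetings, so early patients can finish both treatment and follow-up between two of them.

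**Working it through.** **No figure to reproduce.** The protocol gives no event rate, accrual rate or operating characteristic for the trigger, and n=20 is described as a feasibility number. The check is of the text and the timing, plus an illustration on stated assumptions.

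**Timing.** The Overview gives 4 + 12 + 8 = 24 weeks, or 24 × 7 = 168 days. Section 11 gives 30 + 90 + 60 = 180 days. Both agree with about 6 months per patient, roughly half of a 12-month meeting interval.

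**Who is told of an SAE**

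| Recipient | Route in section 7 | Time |
|---|---|---|
| IRB | direct | 24 hours |
| Manufacturer | if the IRB safety commission decides | decision within 48 hours |
| PI and clinical team | they hold the CRF records | – |
| DSMB | none stated | – |

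**How far the reading matters.** Assumptions: Poisson events; AE rate 0.05 to 0.30 and SAE rate 0.002 to 0.02 per patient-month; N patients constantly under observation for 12 months; counts study-wide.

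For mean m in a window, P(more than 2) = 1 − e^(−m)(1 + m + m²/2) and P(at least 1) = 1 − e^(−m). Over k windows, P(fires at least once) = 1 − (1 − p)^k, with k = 12 monthly or 4 quarterly.

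Worked case, N = 20 at the lowest rates:
- AE limb: m = 20 × 0.05 = 1; p = 1 − 2.5e^(−1) = 0.0803; over 12 months 1 − 0.9197^12 = 0.634.
- SAE limb (at least one in a quarter): m = 3 × 20 × 0.002 = 0.12; over 4 quarters 1 − e^(−0.48) = 0.381.
- Either limb, taken as independent: 1 − 0.366 × 0.619 = 0.773.

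Probability of firing at least once in 12 months, lowest to highest rates:

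| Reading | N = 5 | N = 10 | N = 20 |
|---|---|---|---|
| More than 2 AEs in a month, *or* at least 1 SAE in a quarter | 0.14–0.98 | 0.34 to >0.99 | 0.77 to >0.99 |
| More than 2 SAEs in a quarter | <0.015 | 0.0001–0.09 | 0.001–0.40 |
| More than 2 SAEs in a month | <0.002 | 0.00002–0.014 | 0.0001–0.09 |

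Two cautions apply. First, 20 patients at about 6 months each give 120 patient-months, an average of 10 under observation over a year. The N = 20 column is therefore an upper case over 12 months. At N = 10 with middle rates (0.1 and 0.005), the *or* reading gives 0.80. Second, SAEs are also AEs, so the limbs are positively related and independence somewhat overstates the combined probability. In the worked case it lies between 0.63 (the AE limb alone) and 0.77.

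**Per patient or study-wide.** If more than 2 AEs in a month must occur in one patient, m is 0.05 to 0.30 and p is 0.00002 to 0.0036 per patient-month. Over all 120 patient-months, 1 − (1 − p)^120 = 0.002 to 0.35. The AE limb counted study-wide at N = 10 gives 0.16 to >0.99 over a year with the same 120 patient-months. The unstated unit therefore matters even if the conjunction is corrected.

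**The case against.** The strongest reply is that the sentence has a one-letter slip. With *or* for *of* it becomes an ordinary two-limb rule that uses every word, and two event types with two windows are then no defect. This is the likeliest reading, and much of the reply stands. It does not supply the unit or the counter, and a safety threshold should not rest on a reader's guess.

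Second, *severe AE* is expressly defined in section 7. That also stands: the label is unconventional, since the definition is one of seriousness, but it has one stated meaning. Section 3 need only point to it.

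Third, the DSMB is not shut out. It convenes as often as necessary, its members must be satisfied with the timeliness of the data, and the PI and the IRB can both request a meeting at any time. The IRB has every SAE within 24 hours, and the PI's team holds the AE records and could do the counting. A reader might infer that the DSMB cannot meet or act between annual meetings; these provisions say otherwise. What remains is that the route is discretionary and the PI shares the decision to hold the meeting.

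Fourth, a reader might take this trigger for the only event-driven safety review in the plan. It is not: the IRB safety commission acts on each SAE, at least on forwarding it, and investigators must document their review of each safety report. It is the only automatic trigger for a DSMB meeting.

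Finally, triggers and stopping guidelines are to be discussed at the initial DSMB meeting. That may settle the matter in practice, but the protocol neither gives the result nor requires that meeting before the first dose.

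**Conclusion.** Both gaps are real and can be seen from the text alone. The trigger cannot be applied as written, and no stated step brings an SAE to the DSMB. The DSMB therefore need not learn of an SAE before its annual meeting unless the PI or the IRB chooses to request one.

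The size is only illustrative, because every rate is assumed. Under the *or* reading, counted study-wide, the trigger would usually fire at least once a year at full enrolment (0.77 to above 0.99 with 20 under observation), less surely with fewer patients. Under readings that count only SAEs it would rarely fire. It would be wrong to conclude that the trigger can never fire: that needs an SAE-count reading, few patients under observation, or nobody counting. Nor should one ratio between readings be quoted as the size of the problem. Large ratios come from readings such as more than two SAEs in a quarter, which drops the monthly window from the sentence, and from comparing monthly with quarterly probabilities.

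This should be corrected because safety is the primary criterion and the change costs almost nothing. It does not put the design in doubt.

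**What to change.** 1. **Section 3.** Replace the trigger sentence with one readable rule; a two-limb *or* rule is acceptable. For each limb state the event type by reference to the section 7 definitions, the count, the time window, whether counting is per patient or study-wide, and who keeps the tally and tells the DSMB. The investigators and the DSMB set the values.
2. **Section 7.** Add the DSMB chair as a recipient of each 24-hour SAE notice, and name the DSMB in the closing paragraph on communication so that it agrees with section 3.

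Cost: two sentences and one more addressee on a notice that is already sent. No new data, visits or analyses are needed.
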